5.7. Other Analyses

5.7.1. Immunogenicity Analyses

The analysis of immunogenicity will use the PPI set, PPI modified set and FAS modified set (cf Appendix 2 for analyses sets definitions). Immunogenicity analyses will also be done on the FAS (participants who became infected during the study will be analyzed as a subgroup and shown in the graphs using different colors and symbols). Data will be analyzed by vaccine group, and by vaccine group and age group^a.

Key immunogenicity assay results will also be analyzed for the subgroups defined in Section 5.7.4. Data will be presented by scheduled time point. For the PPI analysis, samples taken outside of the allowed window will be excluded from the tables and graphs (but will be included in the listings and clearly marked as results not included in the PPI analyses). For the FAS analysis, samples taken outside of the allowed window will be included.

Note: analyses that are potentially unblinding at the individual participant level (e.g. graphs showing individual data tied to COVID-19 infection status, especially when the number of COVID-19 infections is low and/or when time of infection is indicated) will be carried out after official unblinding of the trial, or will be carried out exclusively on specific groups (or other clearly defined subgroups) after these are unblinded. Alternatively, prior to unblinding, these analyses can be performed in a completely blinded manner (e.g. tables with only a single column pooling all regimens).

^a As indicated previously, all analyses, including the immunogenicity analyses, will be conducted by actually received vaccine (“as treated” principle). Note that the statistical tables are designed with the planned vaccine regimens as columns. Therefore, participants who receive e.g. “Placebo, Placebo” instead of “Ad26.COV2.S 5x10¹⁰ vp, Placebo” will appear in the “Placebo, Placebo” column. However, to avoid sparse columns, participants who receive e.g. “Placebo, Ad26.COV2.S 5x10¹⁰ vp” (which is not a planned vaccine regimen) will be excluded from the statistical tables. They will be included in the listings, as well as in the programmed patient narratives where they will appear as “Subjects with vaccine misallocation”.

5.7.1.1. Parameters

The following humoral and cellular immune responses may be measured. However, not all assays might be available for all immunogenicity analyses covered by this SAP. Further information on which assays will be analyzed in each of the analyses, will be included in the corresponding DPS documents.

Assay	Purpose
Humoral Immunogenicity	
Primary/Secondary/Exploratory endpoints	
SARS-CoV-2 neutralization (VNA)	Analysis of neutralizing antibodies to the wild-type virus and/or pseudovirion expressing S protein
SARS-CoV-2 binding antibodies (ELISA)	Analysis of antibodies binding to SARS-CoV-2 or individual SARS-CoV-2 proteins (eg, S protein)
Exploratory endpoints	
SARS-CoV-2 binding antibodies (ELISA)	Analysis of antibodies binding to the SARS-CoV-2 N protein, if such an assay is available
SARS-CoV-2 binding antibodies (MSD)	Analysis of antibodies binding to the SARS-CoV-2 S protein (different than the assays supportive of the secondary objectives) and the RBD of the SARS-CoV-2 S protein
Functional and molecular antibody characterization	Analysis of antibody characteristics including Fc-mediated viral clearance, avidity, Fc characteristics, Ig subclass and IgG isotype
Passive transfer	Analysis of immune mediators correlating with protection against experimental SARS-CoV-2 challenge in a suitable animal model
SARS-CoV-2 neutralizing antibodies	Analysis of neutralizing antibodies against emerging SARS-CoV-2 variants
Cellular Immunogenicity	
Exploratory endpoint	
Flow cytometry (ICS)	Analysis of T-cell responses to SARS-CoV-2 S protein, and/or other protein peptides by intracellular cytokine staining (ICS) including CD4 ⁺ /CD8 ⁺ , IFN γ , IL-2, TNF α , IL-4, IL-5, IL-13, and/or other Th1/Th2 markers.
Gene expression analysis	Analysis of gene expression by RNA transcript profiling

5.7.1.2. Handling of Missing and/or Unquantifiable Immune Response Data

Missing immune response data will not be imputed.

Values below the lower limit of quantification (LLOQ) or limit of detection (LOD) will be handled as follows:

- Calculation of geomean and median:
 - o values <LLOQ are imputed with LLOQ/2.
- Calculation of fold increases from baseline:
 - o values <LLOQ are imputed with LLOQ.

Values above the upper limit of quantification (ULOQ) will be handled as follows:

- Calculation of geomean and median:

- o Values >ULOQ are imputed with ULOQ.
- Calculation of fold increases from baseline:
 - o Values >ULOQ are imputed with ULOQ.

5.7.1.3. Handling of changes in assay status throughout the study conduct

In case of changes in assay status, from “qualified” to “validated”, the LLoQ and ULoQ are likely to change as well. If this should happen, then the SDTM database will contain records pertaining to the assay in the qualified status and records pertaining to the validated status, and the LLoQ and ULoQ values will also differ.

The statistical analysis will use the LLoQ and ULoQ values associated with the validated assay and will retrospectively apply these on all the data pertaining to the assay, including the data obtained while the assay status was “qualified”. This may imply that data received, statistically analyzed, and presented at an earlier time may change. Graphical displays will show the eventually used LLoQ and ULoQ values. Graphs and tables will have an additional footnote, that reflects the assay status.

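### If validation widens the assay range, SAP 5.7.1.3 gives unsupported values to qualified-status results held only as below LLOQ or above ULOQ

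*SAP*

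**What the plan says.** SAP 5.7.1.3 expects that on validation "the LLoQ and ULoQ are likely to change as well", and that "the SDTM database will contain records pertaining to the assay in the qualified status and records pertaining to the validated status", with different limits. The rule follows: "The statistical analysis will use the LLoQ and ULoQ values associated with the validated assay and will retrospectively apply these on all the data", "including the data obtained while the assay status was" qualified. The section warns: "This may imply that data received, statistically analyzed, and presented at an earlier time may change". Its safeguards concern display. Graphs show the limits finally used, and "Graphs and tables will have an additional footnote, that reflects the assay status".

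The limits drive the analysed values:

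- **Imputation (SAP 5.7.1.2).** For geometric means and medians, "values <LLOQ are imputed with LLOQ/2". For fold increases the substitute is the LLOQ itself. At the top end, "Values >ULOQ are imputed with ULOQ" in both cases.
- **Positivity and response (SAP 5.7.1.5.1).** A sample is positive if it exceeds the LLOQ. A post-baseline sample is a responder if baseline is at or below the LLOQ and the sample is above it, or if baseline is above the LLOQ and the rise is at least 4-fold. S-ELISA follows the same rules as VNA.

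The SAP does not give the limits or say which way they will move. Nor does it say whether a VNA or ELISA result outside the qualified limits is kept as a number or only as below/above.

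**The concern.** A result known only to lie below the qualified LLOQ cannot be placed against a lower validated LLOQ, because its true value may sit between the two. A result known only to exceed the qualified ULOQ cannot be raised to a higher validated ULOQ. The rule does both, because it covers all data without condition.

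Serological response and GMT/GMC are adult primary endpoints (Protocol section 3, SAP 5.3). The log titres also feed the geometric mean ratios against the 5×10^10 vp dose, the ELISA-to-VNA ratios, and the dose and interval models (SAP 5.7.1.5.1 and 5.7.1.6). Protocol 9.5 plans interim, primary and final analyses, so status could change between them. If baseline samples were run on the qualified assay and later samples on the validated one, the artefact would follow visit.

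**Working it through.** The plan has no figure to reproduce. The rules come from SAP 5.7.1.2, 5.7.1.3 and 5.7.1.5.1. All limits and distributions below are assumptions.

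**Step 1: direction of change, for a record held only as censored.**

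- LLOQ rises 50 to 100: <50 implies <100. No false value.
- ULOQ falls 3000 to 1500: >3000 implies >1500. No false value.
- LLOQ falls 50 to 25: <50 does not imply <25. The record still becomes 25/2 = 12.5 for geometric means and 25 for fold rises. A true value just under 50 is then up to 50/12.5 = 4-fold too low for the mean, and 50/25 = 2-fold for the fold rise.
- ULOQ rises 3000 to 6000: >3000 does not imply >6000. The record still becomes 6000.

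**Step 2: responder calls.** The last column uses the higher LLOQ and lower ULOQ for all records.

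| Case | Rule in 5.7.1.3 | Numbers held, validated limits | Common narrower range |
|---|---|---|---|
| A. LLOQ 50 to 25; baseline <50 (true 40), post 90 | 40 becomes 25; 90 > 25: responder | 90/40 = 2.25: non-responder | baseline <50, 90 > 50: responder |
| B. LLOQ 50 to 25; baseline <50 (true 40), post 40 on the validated assay | 40 > 25: responder | 40/40 = 1: non-responder | both <50: non-responder |
| C. LLOQ 50 to 25; baseline <50 (true 10), post <50 (true 40) | both become 25: non-responder | 10 ≤ 25, 40 > 25: responder | both <50: non-responder |
| D. ULOQ 3000 to 6000; baseline 1000, post >3000 (true 3500) | 6000/1000 = 6: responder | 3500/1000 = 3.5: non-responder | 3000/1000 = 3: non-responder |

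In B and D the rule creates a response that the common range removes. In A and C no rule can recover the numeric call, because the number is gone. The common range makes the call correct for the limit stated, and the same for every record.

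**Step 3: illustrative size.** Simulation of 400,000 participants. Qualified LLOQ 50; no effective ULOQ; every record qualified-status and held only as censored; baseline geometric mean 15 (log10 SD 0.35); post-baseline 60 or 200 (log10 SD 0.4); validated LLOQ 25.

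| | Post GM 60 | Post GM 200 |
|---|---|---|
| Post samples with true value 25 to 50 | 25.0% | 5.3% |
| GMT: rule / numbers held / LLOQ 50 throughout | 44.6 / 58.2 / 59.6 | 187.8 / 199.4 / 196.6 |
| Responder rate: rule / numbers held | 54.4% / 65.3% | 89.6% / 88.3% |
| Calls differing from numbers held | 25.9% | 9.2% |

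Check: moving the imputed value from 50/2 to 25/2 multiplies the GMT by 2^(−f), where f is the share below 50. For GM 60, f = Φ((log10 50 − log10 60)/0.4) = Φ(−0.198) = 0.42, and 59.6 × 2^(−0.42) = 44.5. For GM 200, f = Φ(−1.505) = 0.066, and 196.6 × 2^(−0.066) = 187.8. Both agree with the simulation.

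**Step 4: a wrong value and a changed call are different things.** In Step 3 no call changes from the one at the qualified limit (0%). With the LLOQ doubled to 100, no call differs from the numeric call, yet 28.3% and 17.1% of calls change from those at the qualified limit. An example is baseline 60, post 120: 120/60 = 2, a non-responder at LLOQ 50, becomes a responder at LLOQ 100 because 60 is now below the limit.

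**The case against.** The strongest reply is that nothing in the documents says VNA or ELISA results lose their numbers. SAP 5.7.1.3 can be read as re-deriving stored values under new limits, which is uniform re-censoring and creates no false value. For ICS, SAP 5.7.1.5.2 receives numbers below the limit and substitutes only for display. That is a different assay, so it is suggestive only. SAP 5.6.2 has a rule for safety laboratory results that arrive as text without a number. This shows the authors know such records exist, but the humoral sections have no counterpart, so it cuts both ways. The direction of any change is also undocumented, and the status change itself is only a possibility.

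No immunogenicity hypothesis is tested (Protocol 9.1, SAP 5.7.1.4), and SAP 5.7.1.6 calls the modelling explorative. One set of limits for all records is a defensible aim, both record types stay in the database, and SAP 5.7.1.5.1 leaves room for updated rules in the Data Presentation Specifications, which are not among the documents.

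All of this stands, and it makes the point conditional. It does not remove it. The rule is written for all data without asking whether a number exists, and a footnote or a displayed limit does not correct an imputed value.

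**Conclusion.** The point holds conditionally. The rule gives unsupported values only if (a) assay status changes during the study, (b) the validated range is wider at one end or both, and (c) qualified-status results outside the qualified limits are held only as censored. Under (a) to (c), geometric means, fold rises and responder calls can be wrong. If (b) or (c) fails, no false value arises.

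A reader might infer that qualified-status results are already stripped of their numbers, so that validation will falsify titres and flip responder status. The documents do not support that: storage and direction are both unstated, and Step 4 shows that false values and flips need not occur together. Nor can the simulated percentages, or the 2^(−f) factor, be read as the expected error in this trial. They rest on assumed limits, distributions and complete censoring, and 2^(−f) compares two imputations rather than an imputation with the truth.

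The affected summaries are descriptive, but they include the adult primary humoral endpoints. The change is worth making before a status change enters an analysis.

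**What to change.** Amend SAP 5.7.1.3 as follows:

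1. State, for each assay, whether qualified-status results outside the qualified limits are held as numbers or can be re-derived from stored raw data.
2. Where a number exists or can be re-derived, apply the validated limits as now planned.
3. Where records for an assay are held only as censored at the qualified limits and the validated range is wider, use the higher LLOQ and the lower ULOQ for all records of that assay in that analysis. Use the same limits for imputation, positivity and responder status.

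The cost is SAP wording and one derivation rule. Under item 3 the quantifiable range narrows: some values quantified by the validated assay are treated as censored, and some validated positives become negatives. If numbers exist throughout, or the validated range is narrower, nothing changes from the present plan.

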5.7.1.4. Immune Response Analysis

No formal hypothesis on immunogenicity will be tested.

5.7.1.5. Immunogenicity against the insert

5.7.1.5.1. Humoral assays

For VNA (both wild-type virus and pseudovirion expressing S protein, as available), the following statistics will be calculated: N, geometric mean and corresponding 95% CI of the actual values, fold increase from baseline, fold increase from pre-dose 2 (for time points after dose 2), fold increase from pre-antigen presentation (for time points after the antigen presentation), difference to Ad26 5e10: GMR (95% CI) for Geometric mean and GMR (95% CI) for Geometric mean increase from Baseline.

For the calculation of the geometric mean and its corresponding 95% CI, the arithmetic mean and its corresponding 95% CI are calculated on the \log_{10} transformed values. These values are back transformed to provide the geometric mean and its corresponding 95% CI.

For wild-type and pseudovirion VNA separately:

- A sample will be considered positive if the value is strictly greater than the LLOQ (>LLOQ).
- Responder definition. A post-baseline sample will be considered a responder if at least one of the following conditions is satisfied:
 - The baseline sample value is less than or equal to the LLOQ (\leq LLOQ) and the post-baseline sample value is strictly greater than the LLOQ (>LLOQ)
 - The baseline sample value is strictly greater than the LLOQ (>LLOQ) and the post-baseline value represents an at least 4-fold (\geq 4-fold) increase from the baseline sample value.

Actual values are tabulated and shown as dot plots with dots for participant values, and the corresponding geometric mean and 95% CI per time point for each assay. In addition, GMT plots over time, combining the regimens in one graph (without individual participant dots) will also be generated.

Participant profiles of the actual values over time will be graphically presented.

Reverse distribution curves of the actual values are provided for selected time points.

In the graphs, original values will be displayed on the \log_{10} scale.

Further details and/or updated rules will be provided in the DPS.

For **S-ELISA**, the same as above applies.

The ratio of binding antibodies (S-ELISA) to wild type VNA, and the ratio of binding antibodies (S-ELISA) to pseudovirion expressing S protein VNA will be calculated for each time point. Values <LLOQ will be imputed with LLOQ for the calculation of the ratios. In addition, the ratio of the fold increase from baseline in binding antibodies (S-ELISA) to the fold increase from baseline in wild type VNA, and the ratio of the fold increase from baseline in binding antibodies (S-ELISA) to the fold increase from baseline in pseudovirion expressing S protein VNA will be calculated for each post-baseline time point. Values <LLOQ will be imputed with LLOQ for the calculation of the fold increase ratios. The following statistics will be calculated and tabulated: N, geometric mean and corresponding 95% CI of the ratio. Graphical displays will also be prepared, showing – for each time point – the geometric mean of the ratio and its 95% CI, together with the individual data points (dot plot).

If a similar assay is performed at different analyzing labs, then separate statistical analyses may be performed.

Scatterplots between humoral assay results will be provided for selected time points. These may include but are not limited to:

- Binding antibodies (S-ELISA) versus wild type VNA
- Binding antibodies (S-ELISA) versus pseudovirion expressing S protein VNA
- Wild type VNA versus pseudovirion expressing S protein VNA

If a similar assay is performed at different analyzing labs, then the statistical analyses may distinguish between these and provide separate scatterplots for each analyzing lab versus the other assay of interest. These scatterplots will display the values as analyzed for the geometric mean calculations, with values <LLOQ imputed with LLOQ (if an LLOQ is defined) and values >ULOQ imputed with ULOQ (if an ULOQ is defined). The LLOQ and ULOQ cut-off values per assay will be visualized in the scatterplots. Spearman correlation coefficients will also be provided (one per scatterplot).

In addition, results for group 4 (High Dose single vaccination) and lower doses with double vaccination (D56 regimen) will be graphically presented and summarized with descriptive statistics.

